### **STUDY OBJECTIVES**

The overall aim is to contribute evidence about the impact of treatment of sleep apnea (with CPAP) on cognitive ability in HIV+ individuals.

The primary objective is to estimate among people with HIV and obstructive sleep apnea, the extent to which 4-7 months of CPAP impacts on cognitive ability (B-CAM), in comparison to individuals who screen positive for OSA but are not participating in the sleep apnea intervention.

An exploratory objective is to identify whether the changes are similar on measured cognitive ability and on self-reported cognitive symptoms.

The explanatory objective is to relate degree of adherence to CPAP to change in cognitive outcomes.

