## **Effect of Continuous Positive Airway Pressure (CPAP) treatment on cognitive ability in HIV+ individuals with obstructive sleep apnea (OSA): A pilot study**

The values to be used will be those collected during the scheduled platform evaluations which occur 9-12 months apart.

- (ii) Self-reported cognitive symptoms will be measured using the C3Q (Communicating Cognitive Concerns in HIV) collected during the scheduled platform evaluations which occur 9-12 months apart.
- (iii) Adherence to the CPAP home treatment will be obtained from the CPAP device directly through its telemonitoring function, which is done by activating modems on CPAP machines and having the data transferred onto the Compliance Management Solutions. The granularity of the data will yield a continuous metric of sleep-minutes of use. Reasons for poor adherence and tolerance will be obtained by telephone contact or at clinical visits with the sleep specialist.
- (iv) Three cohorts will be compared: (i) the intervention cohort comprising all those approached who agreed to enter; (ii) the refuser cohort comprising all those approached who declined entry; and (iii) control cohort comprising eligible persons who were not approached, and hence were not given the opportunity to accept or decline.

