### **Statistical Analysis and Sample**

Basic descriptive statistics will be used to characterize the participants including values on the all outcomes. Each person will be classified as a cognitive responder or not based on change on B-CAM. Responder status will be defined as improvement of  $\frac{1}{2}$  SD in B-

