## **Effect of Continuous Positive Airway Pressure (CPAP) treatment on cognitive ability in HIV+ individuals with obstructive sleep apnea (OSA): A pilot study**

CAM score and C3Q. The analysis will focus on estimating the proportion of responders. A sample size of 30 participants will provide sufficient power for within-group analysis. With the assumption that the outcome is drawn from a binomial distribution with an expected probability of response of 10% (N=3) with no intervention, 30 subjects in the intervention group will allow detection of a positive response, with 80% power and  $p<0.05$ , if 7 or more persons respond (stattrek.com binomial calculator.) The proportion of responders on the different cognitive outcomes will also be estimated.

A secondary analysis will relate adherence to CPAP to change in cognitive outcomes using linear regression adjusting for age, sex, weight, baseline sleep satisfaction.

For between-cohort comparisons of cognitive outcomes, generalized estimating equations (GEE) will be used to permit both the baseline and post-intervention measures to be included along with the within-person correlation. A linear GEE will be used as the outcomes are continuous although a binary response was used for the primary objective. The model will include the indicator variable for cohort (CPAP, refuser, or control), time (assessment 1, 2), as well as confounding variables of age, sex, education, BMI, and comorbidity. As the control cohort will be very much larger than the intervention cohort, statistical comparisons have sufficient power to detect effect sizes of 0.5 or greater, suitable for a pilot study. The parameter estimated from GEE is equivalent to an adjusted effect size (adjusted between cohort effect divided by correlation adjusted standard error).

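### Separate B-CAM and C3Q responder proportions describe group-level similarity but cannot show whether the same people improve on both; a cross-classification of the same participants would

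*Protocol*

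**What the plan says.** The Protocol Summary and Study Objectives both set the aim: "An exploratory objective is to identify whether the changes are similar on measured cognitive ability and on self-reported cognitive symptoms".

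Under Measurement, B-CAM values come from the scheduled cohort evaluations, and the C3Q is tied to the same ones: "Self-reported cognitive symptoms will be measured using the C3Q (Communicating Cognitive Concerns in HIV) collected during the scheduled platform evaluations". Each participant measured on both therefore contributes a pair of changes.

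Statistical Analysis and Sample first bases response on one measure: "Each person will be classified as a cognitive responder or not based on change on B-CAM". The next sentence begins "Responder status will be defined as improvement of" half an SD and ends by naming both measures ("CAM score and C3Q"). Then come "The analysis will focus on estimating the proportion of responders" and, after the sample-size argument, "The proportion of responders on the different cognitive outcomes will also be estimated".

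The section also plans basic descriptive statistics on all outcomes, a linear regression of cognitive change on adherence, and a linear GEE comparing the CPAP, refuser and control cohorts. The within-person correlation in the GEE is between the baseline and post-intervention measurements of an outcome, not between B-CAM and C3Q.

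**The concern.** The question "whether the changes are similar on measured cognitive ability and on self-reported cognitive symptoms" can be read at two levels. At group level it asks whether CPAP moves both measures to a similar degree. At person level it asks whether those who improve on testing are those who report improvement. Two separate proportions address the first descriptively. They say nothing about the second, because they discard the pairing.

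The distinction matters for what follows the pilot. The protocol expects improvement on both ability and symptoms and intends the findings to inform a larger study. Equal proportions from the same responders would suggest that self-report follows measured cognition. Equal proportions with no shared responders would suggest that the two measures pick up different things. The within-group summary named in the protocol would look the same in both situations.

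**Working it through.** **The plan's own figure.** The protocol gives no figure for agreement between the two measures. Its one responder count is 7 or more of 30 against a 10% rate without intervention. That count reproduces: P(X ≥ 7 | n = 30, p = 0.10) = 0.026 and P(X ≥ 6) = 0.073, so 7 is the smallest count with one-sided p < 0.05. Below, 7 of 30 serves only as a convenient illustration. Applying it to the C3Q as well is an assumption.

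**Inputs.** n = 30 (Statistical Analysis and Sample); 7 responders on B-CAM and 7 on C3Q (assumed); o = number who respond on both, unknown, from 0 to 7.

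**Formulas.**
- B-CAM only: b = 7 − o. C3Q only: c = 7 − o. Neither: 30 − o − b − c = 16 + o.
- Agreement = (o + 16 + o)/30.
- Chance agreement = (7/30)² + (23/30)² = 578/900 = 0.642.
- Kappa = (agreement − 0.642)/(1 − 0.642).
- Paired SE of the difference in proportions = √[b + c − (b − c)²/30]/30.

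**Results.**

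| Respond on both (o) | B-CAM only | C3Q only | Neither | Agreement | Kappa | Paired SE |
|---|---|---|---|---|---|---|
| 0 | 7 | 7 | 16 | 16/30 = 53% | −0.30 | √14/30 = 0.125 |
| 3 | 4 | 4 | 19 | 22/30 = 73% | 0.25 | √8/30 = 0.094 |
| 7 | 0 | 0 | 23 | 30/30 = 100% | 1.00 | 0 |

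In every row each measure shows 7/30 = 23% (exact 95% CI 9.9% to 42.3%) and the difference is zero. The proportions do not distinguish the rows.

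**Other equal proportions.**

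| Responders on each | Agreement | Kappa |
|---|---|---|
| 3/30 | 80% to 100% | −0.11 to 1 |
| 7/30 | 53% to 100% | −0.30 to 1 |
| 10/30 | 33% to 100% | −0.50 to 1 |
| 15/30 | 0% to 100% | −1 to 1 |

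**Precision of the added summaries.** Agreement of 16/30 has an exact 95% CI of 34% to 72%. For a correlation of zero between the two change scores, the Fisher interval is tanh(±1.96/√27) = ±0.36.

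**The case against.** *The objective may be about groups only.* It follows a primary objective on how far CPAP affects cognition, so the group reading is natural. On that reading, 23% on each measure is fairly called similar, whoever the responders are. This stands, and it is why the point is an improvement and not an error. The wording does not settle the level, and the person-level reading is left without an analysis.

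*More is planned than proportions.* This is true. The GEE, the adherence regression and the descriptive statistics most naturally cover both measures and bear on the size of change. None relates a person's B-CAM change to that person's C3Q change.

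*The responder definition may be joint.* If response means half an SD on both measures, the joint proportion together with the two separate ones fixes the whole 2×2 table. The preceding sentence bases response on B-CAM alone, however, and no joint proportion is promised. The text is ambiguous, not complete.

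*This belongs in a SAP.* A SAP that is not shown could supply the paired analysis. The protocol does name a summary for this purpose, though, and that summary covers only one reading of the objective.

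*A stronger reading: the plan uses the wrong standard error.* A reader might infer that the two proportions will be compared as if independent. The protocol says only that they will be estimated. It states no test of their difference and no independence assumption. Nor would the independence value, √[2 × (7/30)(23/30)/30] = 0.109, always be wrong: it equals the paired SE at chance overlap (o = 49/30, about 1.6) and is conservative when overlap is higher.

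**Conclusion.** The point holds as a low-cost improvement to an exploratory analysis. The responder proportions describe similarity at group level, and no analysis named in the protocol shows whether the same people improve on both measures. With 7/30 on each, shared responders may number 0 to 7, agreement 53% to 100% and kappa −0.30 to 1.00. These ranges rest on equal counts of 7, on all 30 people having both measures at both visits, and on response being defined separately for each measure.

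A reader might go further and infer that equal proportions could hide complete disagreement. At 7/30 that is not possible: with no shared responders, 16 of 30 people still agree as non-responders. Disagreement in all 30 with equal proportions needs 15/30 on each. The accurate term is no shared responders.

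The primary objective and the 7-of-30 rule are unaffected.

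**What to change.** In Statistical Analysis and Sample, after the sentence on responder proportions, add:

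- Response is classified separately on B-CAM and on C3Q, each by its own half-SD rule. This also removes the ambiguity in the responder definition.
- The same participants are cross-classified in a 2×2 table (both, B-CAM only, C3Q only, neither), with percent agreement or kappa.
- The paired difference in proportions is given with a 95% CI. A score-type paired interval is preferable, because the simple interval has zero width when there are no discordant pairs.
- The correlation between the two continuous change scores is reported.

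It would also help to say in Study Objectives whether similarity is meant for the group, for individuals, or for both.

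The cost is one table and one correlation on data already collected, with no added visits or participants. The drawback is imprecision at n = 30, so these results should be labelled descriptive.

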## **Effect of Continuous Positive Airway Pressure (CPAP) treatment on cognitive ability in HIV+ individuals with obstructive sleep apnea (OSA): A pilot study**

- Screen positive for the presence of OSA with either the Berlin or the STOP-BANG
- Have been on a stable HAART regimen for > 6 months
- B-CAM score ≤ 29
- Have not had a change in medications that could potentially interfere with sleep or cognition in the past 4 months.
- Willing to use CPAP as per instructions
- Able to comply with follow-up visit assessments
- Able to communicate in English or French
- Have at least one remaining visit in the main cohort study

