### **Screening:**

Brain Health Now study participants who screen positive for the presence of OSA, meet inclusion/exclusion criteria based on the information already available as part of the main study questionnaires and who, on initial enrolment, have agreed to be contacted for sub-studies, will be approached for participation. Those who agree to participate and provide informed consent will be referred for a polysomnography (sleep study). Those with confirmed OSA will continue to the intervention phase.

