### **Intervention (CPAP)**

Participants will be evaluated by a sleep specialist who will confirm eligibility for CPAP treatment. Eligible participants will be referred to VitalAire for initiation of treatment, following a standard protocol for use in the home (see Appendix 2). CPAP treatment will continue until the next visit for the main study, between 4-7 months based on the timing of the evaluations, after which the OSA study will end.

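### The adherence regression models change in cognition in people selected on a low B-CAM, but leaves the baseline value of the outcome out of its fixed covariate list

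*Protocol*

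**What the plan says.** The study objectives include an explanatory one: "The explanatory objective is to relate degree of adherence to CPAP to change in cognitive outcomes". The section Statistical Analysis and Sample carries it out: "A secondary analysis will relate adherence to CPAP to change in cognitive outcomes", using "linear regression adjusting for age, sex, weight, baseline sleep satisfaction". The list is explicit, and no other section adds the baseline B-CAM or baseline C3Q to this model.

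Three other statements bear on it.

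- Entry requires a "B-CAM score ≤ 29" (Inclusion criteria), so people are selected on the outcome measure itself.
- Under Screening, those approached must "meet inclusion/exclusion criteria based on the information already available as part of the main study questionnaires".
- Under Measurement, the analysed B-CAM results are cohort-visit results too: "The values to be used will be those collected during the scheduled platform evaluations which occur 9-12 months apart". The score that admits a person is therefore probably also the baseline of that person's change score.

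The between-cohort GEE does use the baseline measurement, as a repeated outcome, but that model does not serve the adherence objective.

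**The concern.** A change score contains the baseline with a negative sign. Someone whose baseline was low partly by chance tends to rise at follow-up without treatment, and an entry ceiling on B-CAM favours such people. Baseline and change are then linked for reasons unrelated to CPAP.

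Adherence is not randomised. If nightly use is also related to baseline cognition, part of the baseline-change link can be carried into the adherence slope. A real dose-response could look weaker or stronger than it is, and an apparent one could arise from nothing. With only one prespecified slope, a reader could not tell whether this had happened. The covariate list is fixed in the protocol itself, so this is a stated model choice and not a detail left open.

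**Working it through.** **Plan's own figure.** None exists for this regression. The protocol's only sizing figure (7 or more responders of 30 against 10%) belongs to the responder analysis.

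**Inputs from the protocol.** About 30 CPAP users; outcome is change; covariates are the four listed; entry by a B-CAM ceiling of 29.

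**Assumed inputs (not in the protocol).** B-CAM and adherence in cohort SD units; true slope 0.20; correlation of adherence with baseline cognition c = 0.3 before the entry cut; the cut falls at the cohort median; retest correlation r = 0.6 to 0.8; B-CAM reliability rel = 0.8 to 0.9 where measurement error is allowed. The variance of baseline among those below a median cut is v = 1 − 2/π = 0.363.

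**Case A: adherence follows the observed score, or all retest instability is real change.** The slope of baseline on adherence among those enrolled is

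k = c·v / (c²·v + 1 − c²) = 0.109 / 0.943 = 0.116.

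Unadjusted slope = 0.20 − (1 − r)·k. Adjusted slope = 0.20.

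- r = 0.6: 0.20 − 0.4 × 0.116 = 0.154
- r = 0.7: 0.20 − 0.3 × 0.116 = 0.165
- r = 0.8: 0.20 − 0.2 × 0.116 = 0.177

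**Case B: adherence follows true cognition and B-CAM carries error.** Let s = r/rel be the stability of true cognition, and vT = 1 − rel·(1 − v) its variance among those enrolled.

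Unadjusted slope = 0.20 + c·√rel·(s·vT − v) / (c²·vT + 1 − c²).

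Adjusted slope = 0.20 + c·√rel·s·(1 − rel) / (1 − c²·rel).

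For rel = 0.8 and r = 0.8: s = 1 and vT = 1 − 0.8 × 0.637 = 0.491. The unadjusted slope is 0.20 + 0.3 × 0.894 × 0.127 / 0.954 = 0.236. The adjusted slope is 0.20 + 0.3 × 0.894 × 0.2 / 0.928 = 0.258.

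| Reliability | r | Unadjusted | Adjusted |
|---|---|---|---|
| 0.8 | 0.6 | 0.201 | 0.243 |
| 0.8 | 0.8 | 0.236 | 0.258 |
| 0.9 | 0.6 | 0.176 | 0.221 |
| 0.9 | 0.8 | 0.205 | 0.228 |

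**Combined.** Against a truth of 0.20, the unadjusted slope runs from about 0.15 to 0.24 and the adjusted slope from about 0.20 to 0.26.

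**Check at n = 30.** Simulated trials with the entry cut and four noise covariates (6,000 per setting) give the same means to within 0.004. The sampling SD of the slope is about 0.13 to 0.18. In Case A, root mean squared error, unadjusted against adjusted, is 0.186 and 0.179 (r = 0.6), 0.163 and 0.161 (r = 0.7), 0.135 and 0.136 (r = 0.8).

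**Sensitivity.**

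- If 0.3 is the correlation among those enrolled, k = 0.3 × √0.363 = 0.181, and the Case A unadjusted slopes become 0.128, 0.146 and 0.164.
- If all retest instability is measurement error (rel = r = 0.6) in Case B, the slopes are 0.261 unadjusted and 0.298 adjusted.
- If c is negative, each bias changes sign. If c = 0, both models give 0.20.
- With no true effect, no entry cut, Case A, r = 0.7 to 0.9 and c = 0.3 to 0.5, the two-sided 5% test rejects in 6% to 16% of trials of 30 unadjusted and in 5% adjusted.

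**The case against.** For an exposure that is not randomised, choosing between a change score and baseline adjustment is a recognised dilemma (Lord's paradox), and neither wins in general. If adherence follows stable true cognition, the change score already removes the stable difference. Without selection its slope is then unbiased, and adjusting for an error-prone baseline creates a bias. In every Case B row above, the adjusted slope is the larger of the two and lies above the truth. This stands. A reader might infer that the planned slope is biased whenever adherence is related to starting cognition, that it is always pulled towards zero, or that adjustment is the cure. The protocol supports none of these.

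It is also true that every numerical input is assumed, that the protocol does not place 29 at the cohort median, and that the biases are small beside a sampling SD of 0.13 to 0.18. With the entry cut, adjustment is roughly neutral for precision.

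A reader might also object that CPAP lasts "between 4-7 months based on the timing of the evaluations" without duration in the model, and that adherence is described only thus: "The granularity of the data will yield a continuous metric of sleep-minutes of use". Whether minutes are totalled or averaged per night, and how months on CPAP enter, is detail that an SAP may supply. It is not an error in the protocol.

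What the objection does not answer is that the plan commits to one of two defensible models and gives the reader no means of seeing whether the choice matters.

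**Conclusion.** The point holds in limited form. The protocol fixes a change-score regression that omits the baseline value of the outcome, in people admitted on a low value of that outcome. If adherence is related to baseline cognition, the single planned slope can be off in either direction. Under the stated assumptions it lies between about 0.15 and 0.24 against a truth of 0.20, and the adjusted slope between about 0.20 and 0.26. These ranges illustrate the issue and do not estimate it, because the protocol reports neither an adherence-baseline relation nor a retest correlation or reliability.

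A reader might take this as a flaw in the study's main within-group evidence. It is not: that evidence is the proportion of responders, and the adherence model is a secondary analysis for an explanatory objective. The responder analysis and the GEE are unaffected. The change is worth making because it is cheap and lets the reader judge the slope.

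**What to change.** In Statistical Analysis and Sample, prespecify for each outcome a second adherence model that adds the baseline value of that outcome: baseline B-CAM in the B-CAM model, baseline C3Q in the C3Q model. Report its slope and confidence interval beside those of the planned change-score model, together with the correlation between adherence and baseline. State in advance that the two models rest on different assumptions, and that a material difference between the slopes will be read as uncertainty about the dose-response and not resolved by picking one.

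No new data are needed, since both baseline values are already collected at cohort visits. The cost is one degree of freedom per adjusted model in about 30 people, and a little extra reporting.

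### The between-cohort GEE lists no cohort-by-time term, so its cohort coefficient is the baseline difference plus half the CPAP effect, not the difference in B-CAM change

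*Protocol*

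**What the plan says.** The between-cohort analysis is in the last paragraph of Statistical Analysis and Sample (Protocol). It states that "generalized estimating equations (GEE) will be used to permit both the baseline and post-intervention measures to be included along with the within-person correlation", so each person contributes two outcome values. The terms follow: "The model will include the indicator variable for cohort (CPAP, refuser, or control), time (assessment 1, 2), as well as confounding variables", the confounders being age, sex, education, BMI and comorbidity. Of the estimate it says: "The parameter estimated from GEE is equivalent to an adjusted effect size (adjusted between cohort effect divided by correlation adjusted standard error"). On power it says that "statistical comparisons have sufficient power to detect effect sizes of 0.5 or greater", without giving the number of controls, the within-person correlation or the power level.

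Study Objectives words the primary objective as the impact of CPAP on B-CAM "in comparison to individuals who screen positive for OSA but are not participating in the sleep apnea intervention". Under Screening, "Those with confirmed OSA will continue to the intervention phase". Under Measurement, the comparison group is a "control cohort comprising eligible persons who were not approached, and hence were not given the opportunity to accept or decline".

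**The concern.** When the baseline score is one of the outcomes, a cohort main effect describes how far apart the cohorts are on average over both assessments, and one of those assessments precedes CPAP. The treatment effect lies in how the gap between cohorts changes, which is the cohort-by-time term. That term is not listed, and nothing else in the protocol supplies it.

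The GEE is the only planned comparison between cohorts, and the primary objective is worded as such a comparison. An analyst who follows the text would report a figure that holds only part of any CPAP effect and all of any pre-existing difference. A baseline difference could then pass for a CPAP effect or hide one. Such a difference is plausible: people who reach CPAP have consented and had OSA confirmed by polysomnography, while controls have only screened positive and were never approached.

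**Working it through.** **Inputs from the protocol.** Two assessments, both as outcomes. Cohort with three levels, time with two, five confounders and no interaction. 30 CPAP users meeting the usage rule. A detectable effect size of 0.5. Montreal participants N = 500.

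**Assumptions, not in the protocol.** Controls m = 150 (range 60 to 470, where 470 = 500 − 30 is a ceiling). Within-person correlation r = 0.7 (range 0.5 to 0.8). SD 1 at both assessments, two-sided 5%, no confounder adjustment, refusers left out of the power figures.

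**Step 1: the protocol's own 0.5.** It cannot be reproduced, because the control number, correlation, power level and coefficient are not given. A plain comparison of two means, with SE = √(1/30 + 1/m), has 61% power at m = 60 and 74% at m = 300 for 0.5 SD.

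**Step 2: what the listed coefficient estimates.** Let b be the CPAP-minus-control difference at assessment 1 and d the CPAP-minus-control difference in change.

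- Difference at assessment 1: b
- Difference at assessment 2: b + d
- Cohort coefficient with main effects only and complete pairs: [b + (b + d)]/2 = b + d/2
- Cohort × time coefficient, if included: (b + d) − b = d

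Linear GEE fits to constructed data (three cohorts in the ratio 30:30:150, control trend 0.10, r = 0.7) gave the same values under independence and exchangeable working correlation:

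| b | d | CPAP coefficient, as listed | CPAP × time, if added |
|---|---|---|---|
| 0 | 0.5 | 0.250 | 0.500 |
| −0.25 | 0.5 | 0.000 | 0.500 |
| −0.30 | 0.5 | −0.050 | 0.500 |
| +0.30 | 0 | 0.300 | 0.000 |

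The time coefficient does not help. With d = 0.5 it was 0.171, a change pooled over cohorts: 0.10 + 0.5 × 30/210 = 0.171. No coefficient in the listed model equals d.

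**Step 3: consequence for power and error.** The mean of a person's two scores has variance (1 + r)/2, and the change has variance 2(1 − r). At m = 150, √(1/30 + 1/150) = 0.200.

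- Cohort coefficient: SE = √0.85 × 0.200 = 0.184
- Cohort × time: SE = √0.60 × 0.200 = 0.155

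| Case | Coefficient | Expected value | Chance of significance | Range over m and r |
|---|---|---|---|---|
| b = 0, d = 0.5 | cohort | 0.25 | 27% | 22–34% |
| b = 0, d = 0.5 | cohort × time | 0.50 | 90% | 61–99% |
| b = 0.2, d = 0 | cohort | 0.20 | 19% | 16–23% |
| the 0.5 read as the cohort coefficient itself | cohort | 0.50 | 77% | 65–87% |

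**Step 4: simulation.** 600 GEE runs per case (exchangeable, robust SE, m = 150, r = 0.7):

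| b | d | Cohort: mean, rejects | Cohort × time: mean, rejects |
|---|---|---|---|
| 0 | 0.5 | 0.246, 30% | 0.504, 91% |
| 0.2 | 0 | 0.211, 22% | −0.003, 7% |
| −0.25 | 0.5 | −0.006, 6% | 0.489, 89% |

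In the last case a model of follow-up score adjusted for baseline gave 0.413. Theory is d + b(1 − r) = 0.5 − 0.25 × 0.3 = 0.425. That model therefore answers a different question when the cohorts differ at baseline.

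**The case against.** The strongest reply is that the sentence names variables and is not a full model formula. Including both assessments suggests that change was the interest, and an SAP, not available for this review, may add the interaction. That is possible. But the protocol goes beyond silence: it lists the terms and names a between-cohort effect as the parameter, and in the listed model that is the cohort coefficient.

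Second, the protocol calls the design single-arm pre-post, centres the analysis on the proportion of responders, and states its hypothesis as 7 or more of 30. This is true, and that analysis is untouched. Being single-group, however, it cannot supply the comparison in the objective.

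Third, Study Design has those offered CPAP selected at random from eligible people, and the B-CAM cut-off applies to controls too, which limits imbalance. Measurement also defines the intervention cohort as everyone approached who agreed, and agreement precedes polysomnography, so whether unconfirmed people are in the GEE's CPAP group is not settled. Both points weaken the argument about b. Neither affects the halving, which is present at b = 0.

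Three limits stand. Exactly one half needs complete pairs: with 20% of follow-up scores missing in one constructed data set the coefficient was 0.21 to 0.23, still not d. The power figures and values of b are illustrative; under the Measurement definition the CPAP cohort could exceed 30, with a diluted average effect. And treating a baseline-adjusted model as secondary is a judgement, since with b = 0 both models target d.

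**Conclusion.** The concern holds. As written, the GEE's between-cohort parameter is b + d/2 with complete follow-up, and no listed term gives the difference in B-CAM change that the objective calls for. This follows from the listed terms and needs no assumption about imbalance. Under the stated assumptions, the cost for a true 0.5 SD effect is about 27% power instead of 90%. A 0.2 SD baseline difference alone gives about 19% significant results, and one of −0.25 SD cancels a 0.5 SD effect. The power statement is ambiguous rather than disproved: if its 0.5 means the cohort coefficient itself, power is about 77%. The point should be fixed, but it does not touch the responder analysis.

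**What to change.** Add cohort × time to the GEE and name the CPAP-versus-control interaction coefficient, the difference in B-CAM change, as the estimated effect. With three cohorts this is one model term with two coefficients; the refuser-versus-control coefficient can be reported alongside. Restate the power sentence for the CPAP interaction coefficient, with the assumed number of controls, within-person correlation and power level. A model of follow-up B-CAM adjusted for baseline can be kept as a sensitivity analysis, noting that it targets d + b(1 − r) when the cohorts differ at baseline.

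The cost is one model term and two sentences, with no new data and no change to the responder analysis.
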